### 2.2 Secondary Objectives include the following:

- 2.2.1 To determine if reduction in TMPRSS2 activity via direct inhibition with Camostat mesilate combined with SOC treatment will increase the proportion of patients alive and free of ventilator use or ECMO at Day 28 as compared to SOC treatment combined with placebo.
- 2.2.2 To determine if the combination of Camostat mesilate combined with SOC treatment will result in a decreased mortality rate at 28 and 56 days as compared to SOC treatment combined with placebo.
- 2.2.3 To determine if time to clinical improvement is reduced in patients receiving SOC treatment combined with Camostat mesilate as compared to SOC treatment combined with placebo.
- 2.2.4 To determine if Camostat mesilate combined with SOC treatment is associated with overall improved clinical status at Days 14 and 28 as compared to SOC treatment combined with placebo.
- 2.2.5 To determine if Camostat mesilate combined with SOC treatment is associated with a reduced length of stay in the hospital as compared to SOC treatment combined with placebo.
- 2.2.6 To determine if Camostat mesilate combined with SOC treatment is associated with reduced duration of:
  - a) mechanical ventilation or ECMO use,
  - b) non-invasive ventilation or high-flow oxygen use, and

- c) supplemental oxygen use as compared to SOC treatment combined with placebo.
- 2.2.7 To compare the safety and toxicity profile of Camostat mesilate combined with SOC treatment as compared to SOC treatment combined with placebo.
- 2.2.8 To determine if treatment with Camostat mesilate combined with SOC treatment is associated with decreased incidence of thrombotic events and bleeding complications as compared to SOC treatment combined with placebo.

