- e. Targeted physical examination will specifically target the pulmonary system, as well as any areas of concern from the medical history or noted on the prior physical examination or indicated by subject systems or other findings as determined by the Investigator or designee.
- f. BP, pulse rate, respiration rate, and temperature. Vital signs will be measured at Baseline, and twice daily at least 8 hours apart while hospitalized, and once daily as an outpatient. Timing of assessments in accordance with institutional SOP for hospitalized patients.
- g. See Appendix I for a list of specific CBC with differential, comprehensive metabolic panel, renal profile, and urinalysis with microscopic tests.
- h. See Section 12.0 for description of scale.
- i. Collect nose or throat swab to measure for the presence or absence of SARS-CoV-2 by a PCR based COVID-19 test. The swabbing site (nose or throat) used for the Baseline evaluation should be maintained for all subsequent assessments of the study. If only one nostril will be sampled, use the same nostril for collections.
- j. SpO2 determined by pulse oximetry with simultaneous recording of FiO2 to be recorded twice daily at least 8 hours apart while hospitalized, and once daily as an outpatient. Timing of assessments in accordance with institutional SOP for hospitalized patients.
- k. A + 3 day window will be allowed.
- l. Patients who are discharged prior to Day 14 will not need to come into the clinic to follow Day 1-14 Test Schedule. Patients will be called by Study Team for remote evaluation and will resume visits on Day 14 unless needing to be seen sooner.
- m. Assess as clinically indicated by the treating physician.
- n. Stool samples can be  $\pm$  1 day and will be collected only if patient is able to produce.
- o. Since patients may improve and be discharged from the hospital at any point during the study period, remote monitoring without an in-person exam may be utilized for all Physical exam and assessments after day 1 in accordance with institutional SOP.

R Research Funded

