## 12.0 Treatment Evaluation Criteria

The ordinal scale used for assessment of the clinical and respiratory status on each day of the study is included below. Each day, the worst (i.e., highest ordinal) score from the previous day will be recorded, i.e., on Day 3, the highest ordinal score from Day 2 is obtained and recorded for Day 2. The scale is as defined by the WHO as follows:

Patient State	Descriptor	Score
Uninfected	No Clinical or Virological Evidence of Infection	0
Ambulatory	No Limitation of activities	1
	Limitation of activities	2
Hospitalized, Mild Disease	Hospitalized, no oxygen therapy	3
	Oxygen by mask or nasal prongs	4
Hospitalized, Severe Disease	Non-invasive ventilation or high flow oxygen	5
	Intubation and Mechanical Ventilation	6
	Ventilation + additional organ support-pressors, RRT, ECMO	7
Dead	Death	8

In addition, patients will be stratified at baseline based on the ordinal scale below. A score of 3-4 is associated with hospitalized with mild disease versus score of 5 is associated with severe disease.

The primary outcome assessment for efficacy will be evaluated based on the number of patients who are alive AND respiratory failure-free at Day 28 after study entry.

Respiratory failure at Day 28 will be defined by clinical diagnosis of respiratory failure corresponding to a score of 5-8 on the above ordinal scale at Day 28. Specifically, respiratory failure is defined by meeting any of the following criteria:

- Requiring ICU admission,
- mechanical ventilation,
- ECMO,
- non-invasive ventilation,
- or high flow oxygen devices,

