**8. Days of supplemental oxygen use:** Oxygen days will be defined as the number of days where the clinical status score is equal to 4-7 for those who have a clinical status score greater than or equal to 4 at study entry. Total number of days will be the sum of all reported days, regardless of whether the days occur consecutively or in disjoint intervals.

**9. Occurrence of adverse events related to treatment:** Adverse Events will be recorded and graded according to CTCAE version 5.0 criteria. Occurrence of grade 3 or higher adverse events and SAEs will be assessed between arms.

**10. Development of thrombosis / bleeding complications:** Incidence of arterial and venous thrombosis or bleeding complications will be described in both treatment groups.

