#### Missing Data Considerations

All efforts will be made to minimize the occurrence of missing data. Subjects who discontinue treatment in either arm will be encouraged to remain in the study and to continue with follow-up visits for key outcomes at Day 28 and 56.

For time to event outcomes, subjects who are lost to follow-up or withdrawal from the study prior to Day 28 and prior to observing/experiencing the event will be censored at the time of their last observed assessment.

For duration of non-invasive ventilation/high-flow oxygen, ventilation/ECMO or supplemental oxygen, subjects will be considered to have the event of interest until Day

28 if they have the event of interest at their last follow-up assessment day before Day 28 in the case of lost to follow-up or patient withdrawal. Likewise, if they do not have the event of interest at their last follow-up assessment, they will be considered to not have this event through Day 28.

If the subject is discharged and no further hospitalization data are available, then the subject will be assumed to not have been readmitted to the hospital.

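### Oxygen days are counted only at inpatient scores, so oxygen used at home after discharge drops out and the endpoint is narrower than objective 2.2.6c

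*Combined protocol and SAP*

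**What the plan says.** All references are to the combined protocol and SAP.

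- **Objective 2.2.6c** asks whether camostat shortens the duration of "supplemental oxygen use as compared to SOC treatment combined with placebo". It sets no hospital limit.
- **Section 13.3.2, item 8** defines the endpoint: "Oxygen days will be defined as the number of days where the clinical status score is equal to 4-7". Only patients with an entry score of 4 or more are included, and the days are summed whether or not they are consecutive.
- **Section 12.0** gives the scale. Low-flow oxygen, "Oxygen by mask or nasal prongs", is score 4 and sits under a hospitalized state. The text below the table repeats this: "A score of 3-4 is associated with hospitalized with mild disease". Scores 5 to 7 are also hospitalized states. The ambulatory scores 1 and 2 are separated only by activity limitation; score 1, for example, is "No Limitation of activities".
- **Section 4.0, footnote j** requires SpO2 with FiO2 "to be recorded twice daily at least 8 hours apart while hospitalized, and once daily as an outpatient". Footnote l covers discharge before Day 14: "Patients will be called by Study Team for remote evaluation and will resume visits on Day 14".
- **Section 13.5, Missing Data Considerations** sets a carry-forward rule for durations after loss to follow-up or withdrawal. Patients with the event at their last assessment keep it to Day 28. For the others, "if they do not have the event of interest at their last follow-up assessment, they will be considered to not have this event". A separate rule for discharged patients deals only with readmission.
- **Section 13.5, item 8** plans the median and quartiles in each arm, with no test.

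**The concern.** The endpoint does not measure what its objective names. A patient discharged while still on oxygen moves to a score of 1 or 2, and the count stops at discharge rather than when oxygen stops. The situation is foreseeable: everyone in this analysis enters at score 4 or above, and footnotes l and o of Section 4.0 expect discharge during the treatment period.

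Two things are at stake. First, the reported durations would understate oxygen use in both arms and would partly restate length of stay, which is already a separate endpoint (objective 2.2.5). Second, if discharge on oxygen were more common or earlier in one arm, the two arms could show different oxygen days with no difference in oxygen need, or a real difference could be hidden.

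The carry-forward rule could extend the error. If home oxygen is scored 1 or 2 and that score is taken to mean no oxygen, a patient sent home on oxygen and then lost is fixed as off oxygen to Day 28.

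**Working it through.** The documents give no sample size, effect size or expected value for oxygen days, so there is no planned figure to reproduce. The check is a trace of the definition, followed by a sizing on assumed inputs.

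**Step 1. What is counted after discharge.** Item 8 counts scores 4, 5, 6 and 7. In Section 12.0 all four are hospitalized states. A discharged patient has only the ambulatory scores 1 and 2 (or 0, uninfected), none of which mentions oxygen. Read literally, home-oxygen days contribute zero. No section says how home oxygen should be scored.

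*Constructed example.* Two patients each need oxygen on Days 1–20. One stays in hospital throughout and counts 20 days. The other goes home on oxygen on Day 6. The worst score of that day still counts, so the total is 6 days and 20 − 6 = 14 days are lost.

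**Step 2. Mean undercount in one arm.** Let h be the share of patients discharged on oxygen and e their mean home-oxygen days inside the count window. Then

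mean undercount = h × e.

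Both inputs are assumptions; the documents give neither.

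| h | e = 3 | e = 7 | e = 14 |
|---|---|---|---|
| 10% | 0.3 | 0.7 | 1.4 |
| 30% | 0.9 | 2.1 | 4.2 |

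The range is 0.3 to 4.2 days per patient.

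**Step 3. False difference between arms.** With T for camostat and C for placebo, the false difference in favour of camostat is h_T × e_T − h_C × e_C.

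| Camostat | Placebo | False difference (days) |
|---|---|---|
| 20%, 5 days | 20%, 5 days | 1.0 − 1.0 = 0 |
| 30%, 5 days | 10%, 5 days | 1.5 − 0.5 = 1.0 for camostat |
| 10%, 5 days | 30%, 5 days | 0.5 − 1.5 = −1.0, against camostat |
| 20%, 5 days | 20%, 3 days | 1.0 − 0.6 = 0.4 for camostat |

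**Step 4. Effect on the planned summary.** The plan reports medians, not means. A simulation took true oxygen duration as lognormal (median 9 days, log-SD 0.6, whole days, limited to 1–28; true mean 11.00). It removed e days from a share h of patients, leaving at least one counted day.

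| h | e | Counted mean | Counted median |
|---|---|---|---|
| 10% | 7 | 10.39 | 9 |
| 20% | 7 | 9.77 | 9 |
| 30% | 3 | 10.11 | 9 |
| 30% | 5 | 9.59 | 8 |
| 30% | 7 | 9.16 | 8 |

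The median stays at 9 for shares up to 20% and falls by one day at 30% with 5 or 7 home days. With 30% against 10% and 5 days each, the false mean difference is 0.94 days, a little below the simple 1.0 because at least one day is always counted. The medians are then 8 and 9. The simulation covered 3, 5 and 7 home days, not 14.

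**Step 5. Are the data available?** Footnote j calls for daily outpatient FiO2, which could identify home oxygen, but the endpoint does not use it. The Section 4.0 table has no column between Day 14 and Day 28, so daily outpatient values for Days 15–27 are not clearly scheduled.

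**The case against.** A reader might infer that earlier discharge on home oxygen will show up as a camostat benefit. The documents do not support that. The trial is randomized, double-blind and placebo-controlled (Section 13.1), so discharge decisions are made without knowledge of the arm. If home oxygen is equally frequent and equally long in both arms, the expected false difference is zero. If it differs, the direction is open: more home oxygen in the placebo arm would hide a benefit. A reader might also point to site differences in discharge practice, but site is a factor in the dynamic allocation (Section 6.2.1), so these should lower the count in both arms alike. This part of the objection stands in full, with one limit: blinding does not remove a difference that arises through a drug effect on length of stay, which objective 2.2.5 hypothesizes.

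The plan is also silent rather than explicit on home oxygen. A site could apply the mask-or-prongs descriptor to a patient at home, and the carry-forward rule speaks of the event of interest, not of a score. So it is not certain that every such patient would be recorded as off oxygen. That weakens the claim about what will happen in practice. It does not remove the gap, because inconsistent scoring also needs a written rule.

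No formal inference rests on this endpoint, and every input to its size is assumed. Both statements are correct and limit the weight of the point.

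Finally, a patient who goes from score 4 to score 2 while still on oxygen meets the two-point definition of clinical improvement. A reader might call that a second error. It follows from the scale that the plan attributes to WHO, so it justifies at most an optional sensitivity analysis.

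**Conclusion.** The point holds as a mismatch between endpoint and objective. Read literally, item 8 measures in-hospital oxygen days, while objective 2.2.6c concerns oxygen use without a hospital limit. Both arms are undercounted. The arm comparison is distorted only if the rate or length of home oxygen after discharge differs by arm; this is possible if camostat shortens stay, and the distortion could favour either arm. A bias towards camostat is not established.

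The size is unknown. The figure of 0.3–4.2 days per patient rests on assumed shares of 10–30% and 3–14 home days, all inside the count window. The planned median may move little, but that rests on one assumed distribution and at most 7 home days. The endpoint is secondary and descriptive, and the point does not touch the primary analysis. It should be corrected because the stated rule misses part of its own objective and the correction is cheap.

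**What to change.** 1. In 13.3.2 item 8 and 13.5 item 8, count a day as an oxygen day if the score is 4–7 **or** the patient is out of hospital on supplemental oxygen. Take the second part from the outpatient FiO2 in footnote j, plus a field for home oxygen (yes/no) and its stop date, asked at the remote calls, Day 14 and Day 28. The stop date covers Days 15–27. State the count window and how home oxygen is scored on the ordinal scale.
2. Under Missing Data Considerations, state that carry-forward for this endpoint follows actual oxygen use. A patient last known to be on home oxygen is then carried forward as on oxygen.
3. If home oxygen cannot be collected, rename both the endpoint and objective 2.2.6c as in-hospital oxygen days.
4. Optional: a sensitivity analysis of time to clinical improvement in which discharge while still on oxygen does not count as improvement.

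The cost is SAP wording, one added CRF field and some reliance on patient report. No extra visit is needed.

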### 13.3.3 Exploratory Endpoint(s)

**1. Time to Viral Clearance:** Viral clearance will be assessed at days 1, 7, 14, 28, 56 after study entry and the proportion of patients having viral clearance at each of these days will be estimated as the proportion of patients who are documented as having non-detectable

viral shedding divided by the total number of patients in each treatment arm. Serum and nasopharyngeal assays will be used for this analysis.

#### 13.4 Planned Analyses

##### Primary Analysis

Frequency distributions and chi-square tests will be used to screen for major imbalances in the two randomization groups for qualitative variables; graphical displays including box plots and summary statistics (e.g., mean, median, standard deviation, ranges, etc.) will be used for quantitative variables with t-tests (after appropriate transformations if necessary to meet the assumptions of the methods).

The primary outcome will include the number of patients who are alive AND free from respiratory failure at Day 28 divided by the total number of patients in each arm. This endpoint will be analyzed in a binary fashion using properties of the binomial distribution and will be compared between randomized arms by the use of independent samples Z-test for proportions and a 95% confidence interval will be constructed for the difference between arms. Proportions will also be compared using Cochran-Mantel-Haenszel tests, including the stratification factors of age and baseline disease severity. Multivariable logistic regression models will be used to assess the influence of treatment while controlling for covariates of interest (gender, symptom onset, comorbidities) along with stratification factors. Primary analysis for this efficacy outcome will include all participants who are randomized and received at least 1 dose of study treatment. Participants will be analyzed according to the treatment to which they were randomized.

Efforts to minimize loss to-follow-up will be considerable. However, small amounts of missing data may occur. In such cases, participants without Day 28 outcome data will be excluded from the analysis. Sensitivity analyses will evaluate the impact of making different assumptions about the missing observations.

**Interim analyses:** Two interim analyses will be conducted after 25% and 50% of patients have completed the 28 day study period. The interim analysis will include the below stopping rules for efficacy and futility based on a Lan-DeMets spending function with O'Brien-Fleming boundaries. Occurrence of adverse events will also be evaluated at the interim analysis.

Accrual	Control arm (#)	Camostat arm (#)	Total number (#)	Efficacy boundary (Z scale)	Alpha spent	Futility boundary (Z scale)	Beta spent
25%	33	33	66	+/- 4.33	0.001	+/- 0.007	0.002
50%	66	66	132	+/- 2.96	0.003	+/- 0.34	0.04
100%	132	132	264	+/- 1.97	0.05	+/- 1.97	0.20

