## 13.0 Statistical Considerations and Methodology

### 13.1 Statistical Design

The study design will be a randomized (1:1 ratio), double-blinded, placebo-controlled phase II trial of 264 patients. Randomization will be stratified based on age (< 65 years versus  $\geq$  65 years) and disease severity at study entry (hospitalized with mild disease versus hospitalized with moderate/severe disease). The purpose of this study is to evaluate the efficacy of Camostat mesilate in addition to SOC treatment as compared to SOC treatment combined with placebo with respect to clinical status on Day 28. The proportion of patients alive AND free from respiratory failure at Day 28 will be the primary outcome.

Patients will be analyzed according to their randomization assignment. All patients meeting eligibility criteria who received at least 1 dose of study drug will be included in the analysis.

Formal interim analysis will be conducted after the first 66 patients (33 treated in the treatment arm and 33 in the control group) have completed the 28 Day assessment period. Safety analyses will be done to assess occurrence of any differences in adverse events between the treatment arms. A second interim analysis will occur after 132 patients (66 in the treatment arm and 66 in the control group) have completed the 28 Day assessment period.

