### 13.6 Sample Size

Randomization will be done according to a 1:1 ratio. Based on data from Wang et al, 82% of patients treated with Remdesivir were alive and free from respiratory failure at day 28. In the preliminary report of Remdesivir for the treatment of COVID-19 in 1059 hospitalized patients, approximately 70% of patients treated with Remdesivir were alive and free from respiratory failure at Day 15; Day 28 data are not yet available. Using an expected proportion of 80% for the SOC control arm, this study would require 132 patients in each arm (total of 264 patients). Sample sizes of 132 in each arm achieves 80% power to detect a difference between the group proportions of 12% for the primary endpoint. The proportion in the treatment arm is assumed to be 80% under the null hypothesis and 92% under the alternative hypothesis. The proportion in the SOC arm is 80%. The test statistic used is the two-sided Z-Test with unpooled variance. The significance level of the test is 0.05 (two-sided).

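### The first futility look (±0.007 at 33 per arm) cannot spend its stated beta of 0.002 on a binary endpoint, and the alpha printed beside Z = 4.33 does not match it

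*Combined protocol and SAP*

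**What the plan says.** Section 13.4 (Interim analyses) plans looks at 25% and 50% of patients, with "stopping rules for efficacy and futility based on a Lan-DeMets spending function" of O'Brien-Fleming type. The table gives:

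| Look | Per arm | Efficacy Z | Alpha spent | Futility Z | Beta spent |
|---|---|---|---|---|---|
| 25% | 33 | ±4.33 | 0.001 | ±0.007 | 0.002 |
| 50% | 66 | ±2.96 | 0.003 | ±0.34 | 0.04 |
| 100% | 132 | ±1.97 | 0.05 | ±1.97 | 0.20 |

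On the endpoint, the same section says: "This endpoint will be analyzed in a binary fashion using properties of the binomial distribution". On missing data: "participants without Day 28 outcome data will be excluded from the analysis". Section 13.1 repeats the count of 33 and 33 for the first look. Section 13.6 states: "Sample sizes of 132 in each arm achieves 80% power to detect a difference between the group proportions of 12% for the primary endpoint", with 80% in the control arm and 92% under the alternative. It adds: "The test statistic used is the two-sided Z-Test with unpooled variance".

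The plan does not put the futility inequality into words. It also does not say whether futility is binding, or how ties are handled.

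**The concern.** A band of ±0.007 around zero is far narrower than the gaps between the values that Z can take with 33 binary outcomes per arm. The chance of landing in it then depends on whether an exact tie is possible, and the normal curve no longer describes it. If so, the stated beta of 0.002 misdescribes what the first look costs. A DSMB that relied on it would believe that stopping on a tie sacrifices 0.2% of trials of an effective drug.

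The alpha cell in the same row also looks wrong: 0.001 is far too large for a boundary of 4.33.

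**Working it through.** **Inputs.** Rates 80% and 92%, unpooled Z, two-sided 0.05, 132 per arm (13.6). Looks at 33, 66 and 132 per arm, and the boundaries in the table (13.4).

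**Reading of the futility column.** The ± signs, the two-sided test and the equal final boundaries (1.97 and 1.97) imply a symmetric inner band: futility if |Z| is below the value. After 4.33 and 2.96, the final efficacy boundary for a total alpha of 0.05 is 1.969 if futility is ignored and 1.952 if both bands bind. The printed 1.97 therefore fits a non-binding rule.

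**Step 1: reproduce the table.** The two-sided O'Brien-Fleming-type spending function is 4 − 4Φ(z(1−x/4)/√t).

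- Beta, x = 0.20, z = 1.645: at t = 0.25, 4 − 4Φ(3.290) = 0.0020; at t = 0.5, 4 − 4Φ(2.326) = 0.040. Both match.
- Alpha, x = 0.05, z = 2.241: at t = 0.5, 4 − 4Φ(3.170) = 0.0031, which matches. At t = 0.25, 4 − 4Φ(4.483) = 0.0000147, which does not match the printed 0.001.
- The two-sided p-value at Z = 4.33 is 0.0000149. An alpha of 0.001 corresponds to Z = 3.29.

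The normal-theory drift is 0.12/√((0.16 + 0.0736)/132) = 2.853, so the mean of Z at the first look is 2.853 × √0.25 = 1.43. This gives P(|Z| < 0.007) = 0.0020, cumulative futility of 0.039 by the second look, and power of 0.802. On a continuous scale the design does what it says.

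**Step 2: the same band on binary data.** At 33 versus 33, the smallest non-zero |Z| comes from 16/33 against 17/33:

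(1/33) / √(2 × (16 × 17/33²)/33) = 0.0303/0.1230 = 0.246.

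Only a tie lies inside ±0.007. Its probability under the alternative is

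Σₖ Bin(k; 33, 0.80) × Bin(k; 33, 0.92) = 0.0523,

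about 26 times the stated 0.002. The next wider symmetric set (counts differing by at most one) has probability 0.164. No non-empty symmetric band at 33/33 can therefore spend 0.002.

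At 33 versus 32, the smallest non-zero |Z| is 0.022. Only all-failure or all-success in both arms gives Z = 0, with probability 0.000044.

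**Step 3: the whole design.** Exact binomial recursion with efficacy boundaries 4.33, 2.96 and 1.97, under 80% versus 92%:

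| Case | First-look futility | Cumulative by look 2 | Power |
|---|---|---|---|
| Stated in the plan | 0.002 | 0.04 | 0.80 |
| Both bands acted on, 33/33 | 0.0523 | 0.0849 | 0.778 |
| Both bands acted on, 32/32 | 0.0548 | 0.0874 | 0.776 |
| Both bands acted on, 33/32 | 0.000044 | 0.0409 | 0.806 |
| ±0.34 only | none | 0.0409 | 0.806 |
| No futility stopping | none | none | 0.817 |

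Pooled variance gives the same picture: power 0.777 with both bands and 0.806 with ±0.34 only. For other control rates with the same 12-point gain, the tie probability at 33/33 is 6.0% (70/82), 5.8% (75/87) and 3.8% (85/97).

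**The case against.** The strongest reply is that 0.002 is no slip: it is right under the normal approximation on which the table is built, and what remains is discreteness. That is true, but the plan applies the boundary to a binomial endpoint at 33 per arm, where the approximation fails for so narrow a band.

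Second, the 5.2% needs exactly equal evaluable counts. Dynamic allocation (6.2) does not force equal totals, and missing Day 28 outcomes are excluded. The plan gives no missing-data rate. Assuming 33 allocated per arm and independent missingness of 1%, 2%, 5% or 10%, counts are equal in 57%, 40%, 23% or 17% of trials, and average power is 79.0%, 79.4%, 79.8% or 79.9%. This stands: 77.8% is close to the worst case, and the average loss is about one point or less. First-look futility still averages 1% to 3%, above 0.002. If 13.1 means 33 and 33 completers, the 5.2% case is the planned one.

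Third, the loss arises only if the DSMB acts on a tie, and no section makes futility binding. This also stands. However, non-binding status protects type I error. It does not protect power when the rule is followed.

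Fourth, the alpha cell may be <0.001 with the sign lost. That is plausible, and it makes that part a labelling correction.

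Finally, a one-sided reading of the futility rule (Z at or below 0.007) does not help: it gives 10.4% at 33/33.

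**Conclusion.** The concern holds, with a modest effect. At the planned 33 versus 33 the first futility look stops 5.2% of trials with the assumed benefit, against 0.2% stated. If both bands are acted on, power is 77.8%, which is 2.2 points below the stated 80%. At 33 versus 32 the look does almost nothing and power is 80.6%. One missing outcome therefore decides which rule is in force, and neither delivers the stated beta.

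The result rests on the symmetric reading of the ± values, rates of 80% and 92%, and a DSMB that follows the rule. The 25% alpha cell contradicts its own boundary, but 4.33 is correct and overall type I error does not depend on the cell. The efficacy boundaries, the ±0.34 look and the sample size stand. This should be fixed, but it does not threaten the trial.

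**What to change.** In section 13.4:

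1. Change alpha spent in the 25% row to about 0.000015, or to <0.001.
2. Delete the ±0.007 futility look and keep ±0.34 at 132 patients. Exact power is then 80.6% and cumulative beta 0.041, in line with the stated 80% and 0.04. If the look is kept, state that with equal counts, and if acted on, cumulative beta is about 0.05 and 0.085 and power about 78%. Those figures do not apply to unequal counts.
3. Say in words that futility means |Z| below the tabulated value, and that the rule is non-binding, which the final 1.97 fits.

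The cost is an edit to the 25% row and one or two sentences, with no extra patients. Deleting the look lowers early futility stopping under no effect (80% versus 80%) from 34% to 26%. If the bands are acted on, exact two-sided type I error moves from 0.047 to 0.050. If futility is never acted on, it is 0.052 with or without the change.
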